Appendix 10 Conduct of the Study During the COVID-19 Pandemic

Benefit/Risk Assessment of the Conduct of the Study During the COVID-19 Pandemic

Efficacy results from the 36-month analysis of Debio 1143-201 in LA SCCHN patients have shown antitumor activity of xevinapant. Estimate of LRC at 36 months was 78% (95% CI: 61; 88) in the xevinapant arm versus 56% (95% CI: 34; 73) in the placebo arm, leading to a reduction of LRC failure risk of 54% in the xevinapant group compared to the placebo group (hazard ratio 0.46 [95% CI: 0.19; 1.13], $p=0.0893$).

Xevinapant + CRT treatments also demonstrated a clinically meaningful improvement in PFS versus the control group. Estimate of PFS at 36 months was 72% (95% CI: 56; 84) in the xevinapant arm versus 36% (95% CI: 20; 51) in the placebo arm, reflecting a significant reduction of 67% in the risk of disease progression or death in the xevinapant group compared to the placebo group (hazard ratio 0.33 [95% CI: 0.17; 0.67], $p=0.0019$).

Xevinapant combined with CRT also showed a clinically significant improvement in overall survival vs the control group. Estimate of overall survival at 36 months was 66% (95% CI: 50; 78) in the xevinapant arm versus 51% (95% CI: 35; 65) in the placebo arm, reflecting a 51% reduction in the risk of mortality of any cause in the xevinapant group compared to the placebo group (hazard ratio 0.49 (95%CI: 0.26; 0.92), $p=0.0271$).

To date, the observed safety profile associated with xevinapant given alone or in combination with chemotherapy, CRT, or immunotherapy suggests an acceptable and predictable safety profile of the compound. The observed toxicities were in line with those expected in patients with advanced solid tumors, and/or with those observed in patients treated with a similar combination chemotherapy or CRT regimen. In general, the predominant toxicities were mild and/or mostly reversible, could be monitored by routine clinical examinations and were manageable by dose delay, dose reduction, and/or supportive care.

Based upon the safety data observed thus far, xevinapant doses of up to **CCI** mg/day were safely combined with either chemotherapy, RT, or both. In Study Debio 1143-201, xevinapant was administered to participants with LA SCCHN in combination with cisplatin and standard RT. An increased risk of nausea, mucosal inflammation, dysphagia, weight decrease, radiation skin injury, tinnitus, hyperlipasemia, elevation of transaminase, and Grade 3 anemia was observed versus placebo. Nevertheless, the safety profile of xevinapant used in combination with CRT remained acceptable and manageable.

The COVID-19 pandemic globally affected the society in many aspects, including the conduct of clinical studies. While cancer patients are a subpopulation at increased risk during the pandemic, they are also a patient population in urgent need of receiving treatment for their disease. Therefore, during the COVID-19 pandemic, the decision to start cancer treatment is very individual and relies on a thorough benefit/risk analysis per patient by the treating physician.

Recommendations for Mitigation Measures During the COVID-19 Pandemic

Considerations for participants' eligibility

The safety of the clinical study participants is of primary importance. The individual benefit-risk ratio should be carefully evaluated for each of the potentially eligible participants, since participants with cancer are at higher risk of severe complications caused by COVID-19. Furthermore, special attention should be paid to those participants with additional risk factors for more serious COVID-19.

Recommendations for the initiation of study intervention

In the context of the study protocol exclusion criteria #6 “Other infections (viral [including COVID-19] and/or bacterial and/or mycotic) requiring systemic treatment”, a COVID-19 diagnostic test (PCR or antigen test) is mandatory during Screening, except for participants who have completed vaccination against SARS-CoV-2 or who have recovered from confirmed COVID-19 at Screening, as per local regulations. The result of this diagnostic test should be available before randomization. If the test is positive, irrespective of the absence or presence of symptoms, the initiation of the study intervention should be postponed until any existing symptoms have resolved and a follow-up test (PCR or antigen test) is negative.

If initiation of treatment is postponed, study intervention should not be started before a negative COVID-19 test result. Additionally, in case of symptoms, study intervention initiation should be postponed until resolution of fever without the use of fever-reducing medications and improvement in respiratory symptoms (e.g. cough, shortness of breath).

Once the informed consent has been signed, all confirmed COVID-19 cases should be reported as an AE even if they are asymptomatic.

Recommended study procedures in case of COVID-19 pandemic in study site area

Recommendations for the management of participants enrolled in the study during the COVID-19 pandemic are listed below. There might be specific national legislation and guidance in place, which can be considered to complement these recommendations, or may take priority over these recommendations.

In case the hospital facility cannot ensure the safety of the study participants during the visits despite of all efforts made, the following procedures must be considered:

Certain study assessments, especially those related to safety, such as ECGs and blood monitoring (Section 8.2) can be exceptionally performed in institutions other than the study site. More specifically, these assessments can exceptionally be performed at different local laboratories or relevant clinical facilities authorized/certified (as legally required nationally) to routinely perform such tests, if this can be done within local rules on social distancing.

This decision will be at the Investigator's discretion, based on an assessment of potential risk of SARS-CoV-2 infection between a visit to the study site versus a visit to another institution.

Additionally, the above exception should also be considered in case of operational limitations at the site e.g. overburden of the site laboratories due to management of COVID-19 patients.

Assessments done in other institutions will be accepted for study purposes if the data generated by these institutions are included in the participants medical records to allow for study data entry and monitoring.

To minimize the likelihood that the participant might run out of study intervention in case she/he has to skip visits due to the risk of COVID-19, the study intervention may be shipped from sites to the participant's residence according to the site's internal procedures, local laws/regulations for privacy data protection, and according to the product specifications.

The sites must inform the CRO and the Sponsor immediately about the implementation of any of the above adaptations or measures.

In case a participant becomes infected with SARS-CoV-2 during the treatment period, the Investigator must consider any study treatment modification in the best interest of the participant and in accordance with the protocol (Section 6.5.1.2;Table 7 and Table 8). This includes an evaluation of potential DDI if the use of concomitant medications is necessary to manage COVID-19 (Section 6.8). Any modification to study treatment or use of concomitant medication must be clearly documented in the participant's medical records and reported in the study eCRF.

Note: in case of study intervention discontinuation, it is important that the participant remains in the follow-up of the study to not jeopardize the primary and secondary endpoints data collection.

Recommendations for the implementation of Remote Source Data Verification (rSDV)

In exceptional and justified cases and only if strictly necessary, rSDV can take place. For Germany specific: In case of rSDV implementation, the supplementary recommendations of BfArM and PEI to the European Guidance on the Management of Clinical Trials during the COVID-19 (Coronavirus) Pandemic will be followed.

Conclusions

The above measures are considered adequate to further minimize the risks to participants during the COVID-19 pandemic. Thus, the benefit/risk for the study during the COVID-19 pandemic is considered to remain favorable.

Any activity related to implementation of these measures will be captured in the Trial Master File for the study and will be described in the clinical study report.

These rules will not apply once the COVID-19 pandemic will be declared to have ended in the applicable country.

Appendix 11 Country-specific Requirements

Not applicable

Appendix 12 Protocol Amendment History

The information for the current amendment is on the title page.

**List of Abbreviations and Definition of Terms**

AE	Adverse Event
ATC	Anatomical Therapeutic Chemical classification
CDISC	Clinical Data Interchange Standards Consortium
CI	Confidence Interval
CR	Complete Response
(e)CRF	(electronic) Case Report Form
CRR	Complete Response Rate
CSR	Clinical Study Report
DLT	Dose Limiting Toxicity
ECG	Electrocardiogram
ECOG	Eastern Cooperative Oncology Group
EDMS	Electronic Document Management System
EEA	European Economic Area
EudraCT	European Union Drug Regulating Authorities Clinical Trials
FAS	Full Analysis Set
FU	Follow-up
HR	Hazard Ratio / Heart Rate
HRQOL	Health Related Quality of Life
IAP	Integrated Analysis Plan
ICE	Intercurrent Event
ICH	International Conference on Harmonization
MedDRA	Medical Dictionary for Regulatory Activities
NA	Not Applicable
NCI-CTCAE	National Cancer Institute – Common Terminology Criteria for Adverse Events
ORR	Objective Response Rate
OS	Overall Survival
PD	Progressive Disease or Protocol Deviation / Pharmacodynamics
PFS	Progression Free Survival
PK	Pharmacokinetics
PR	Partial Response

SAE	Serious Adverse Event
SCR	Screening analysis set
SD	Stable Disease / Standard Deviation
SDTM	Study Data Tabulation Model
SMC	Safety Monitoring Committee
SOC	System Organ Class
TEAE	Treatment-Emergent Adverse Event
TLF	Tables, Listings, and Figures
WHO-DD	World Health Organization Drug Dictionary

### 3 Modification History

Unique Identifier for Version	Date of IAP Version	Author	Changes from the Previous Version
1.0	22Apr2024		NA
2.0	14Mar2025		Add Section 7.1 Overview of Planned Analyses after discontinuation of Xevinapant trials

### 4 Purpose of the Integrated Analysis Plan

The purpose of this IAP is to document technical and detailed specifications for the analysis of data collected for protocol MS202359\_0025. Results of the analyses described in this IAP will be included in the CSR, except when otherwise stated. Additionally, the planned analyses identified in this IAP may be included in regulatory submissions or future manuscripts. Any post-hoc, or unplanned analyses performed to provide results for inclusion in the CSR but not identified in this prospective IAP will be clearly identified in the CSR.

The IAP is based upon Section 9 (Statistical considerations) of the study protocol and protocol amendments and is prepared in compliance with ICH E9. It describes analyses planned in the protocol and protocol amendments.

The wording used in this IAP is chosen to best match the respective wording in the study protocol template, the CSR template, CDISC requirements and special requirements for table layouts. Therefore, the following approach is used:

Generally, the term ‘participant’ will be used instead of ‘subject’ or ‘patient’. However, in tables and listings the term ‘subject’ will be used to match CDISC requirements, except for in-text tables where ‘participant’ will be used to match the CSR and protocol templates. Similarly, the term ‘study intervention’ will be used in this document instead of ‘treatment’ to match protocol and CSR templates, however, tables and listings will use ‘treatment’ for brevity reasons. Exceptions from this rule are commonly used terms like “on-treatment”, “treatment-emergent”, “treatment policy”, “subject-years”, “by-subject”, or names of eCRF pages like “Treatment Termination” page.

## 5 Objectives and Estimands

Objectives	Endpoints	Further Estimand Attributes	Ref. #
Primary			
To evaluate tolerability of xeviprant when added to weekly cisplatin-based CRT in LA SCCHN	Occurrence of DLT-like events (See Section Error! Reference source not found. for definition)	
Population: Treatment naïve patients with LA SCCHN (Stage III, IVA, or IVB) with histologically confirmed diagnosis in at least 1 of the following sites: oropharynx (HPV-negative), hypopharynx, and larynx, eligible to receive weekly cisplatin-based concurrent CRT
 
Treatment: xeviprant, weekly cisplatin, and IMRT followed by xeviprant monotherapy
 
Intercurrent Event Strategy:
 
 
Discontinuation/interruption/delay of xeviprant/cisplatin treatment (> 40% of planned cumulative dose missed in DLT-like assessment period) due to reasons other than treatment-related AE (composite strategy: to be considered as DLT-like event)
 
RT delay > 2 weeks during the DLT-like assessment period due to reasons other than treatment-related AE (composite strategy: to be considered a DLT-like event)
 
 
Population-Level Summary:
 
 
DLT-like event rate and associated CI
 
Standard summary statistics
 
	1
Secondary			
To characterize safety of xeviprant when added to weekly cisplatin-based CRT in LA SCCHN	Occurrence of AEs and treatment-related AEs Absolute values and changes in eGFR	Population/Treatment: Same as #1	2
To evaluate clinical activity parameters using Response Evaluation Criteria in Solid Tumors (RECIST) v 1.1	Objective Response (OR) according to RECIST 1.1 assessed by Investigator	Population/Treatment: Same as #1 
Intercurrent Event Strategy:
 
 
Discontinuation of treatment: ignoring the intercurrent event (treatment policy strategy)
 
Start of new anticancer therapy: ignoring assessments after the intercurrent event (while not treated with new anticancer therapy strategy)
 
Progression according to RECIST 1.1: assessments up to the intercurrent event (while not progressed strategy)
 
 
Population-level Summary: Response rates (i.e. CRR, ORR) including associated statistics
	3

Objectives	Endpoints	Further Estimand Attributes	Ref. #
	PFS according to RECIST 1.1 assessed by Investigator	Population/Treatment : Same as #1 Intercurrent Event Strategy : 
 
Death within 2 missing scheduled tumor assessments after last evaluable assessment or start of study intervention will be considered as event (composite strategy)
 
Discontinuation of treatment: ignoring the intercurrent event (treatment policy strategy)
 
Start of subsequent anticancer therapy: ignoring events after the start of a new anticancer therapy (hypothetical strategy)
 
 Population-level Summary : Kaplan-Meier estimates including associated statistics	4
	Locoregional control (LRC) according to RECIST 1.1 assessed by Investigator	Population/Treatment : Same as #1 Intercurrent Event Strategy : 
 
Death: Assessments before death will be used (treatment policy strategy)
 
Discontinuation of treatment: ignoring the intercurrent event (treatment policy strategy)
 
Start of new anticancer therapy: ignoring events after the start of a new anticancer treatment (hypothetical strategy)
 
 Population-level Summary : Same as #4	5
To evaluate time to subsequent cancer treatments in participants treated with xevinapant when added to weekly cisplatin-based CRT in LA SCCHN	Time to subsequent systemic cancer treatments	Population/Treatment : Same as #1 Intercurrent Event Strategy/ Population-level Summary : Same as #5	6

## 6

## Overview of Planned Analyses

The following analyses are planned for this trial:

- Safety Monitoring Committee (SMC) analyses

- Primary analysis
- Follow-up analyses to report further efficacy and safety data

## 6.1 Analyses for SMC meetings

The Safety Monitoring Committee (SMC) will recommend on the continuation, modification or stop of the study based on safety data and available PK and available PD data (only when PK data is reviewed). Once all planned number of participants have been treated for at least 5 weeks (DLT-like assessment period) or have experienced a DLT-like event, a data snapshot will be taken for provision of SMC outputs. There will be no data cut-off applied.

Details of analyses for SMC meetings will be specified in Appendix 1.

## 6.2 Primary Analysis

This analysis will be the main analysis. All planned analyses identified in the Clinical Study Protocol and in this IAP will be performed and the database is locked for the analysis.

The cut-off for the primary analysis will be when CCI [REDACTED] meet at least 1 of the following criteria:

- Experience at least 1 DLT-like event, regardless of the administered amount of study intervention/completion in the DLT-like assessment period.
- CCI [REDACTED] of xevinapant and cisplatin during the DLT-like assessment period and either complete the DLT-like assessment period or discontinue study.

## 6.3 Follow-up Analysis

An extract of the primary analyses as specified in the TLF table of contents will be done in the follow-up analysis when the End of Study has been reached.

# 7 Changes to the Planned Analyses in the Clinical Study Protocol

## 7.1 Overview of Planned Analyses after discontinuation of Xevinapant trials

A review of the TrilynX study (MS202359\_0006) data suggests that the experimental arms with Xevinapant demonstrated either lower efficacy compared to the control group or limited potential for added benefit over standard of care.

Consequently, the scope of analyses for this study (MS202359\_0025) has been reduced. The analyses outlined in Section 6 will not be conducted as originally planned. However, following analyses will be performed instead:

- an analysis for the first SMC with 6 patients,

- an analysis using the primary analysis DBL date of 20-SEP-2024 for a synoptic CSR.

The analyses considered relevant for a synoptic CSR are listed below:

- Study Subject Data:
  - Participant disposition
    - Subject Disposition Status
    - Analysis Sets
  - Enrollment details
  - Demographic Characteristics
  - Medical History
  - Other Baseline characteristics
    - Disease History
  - Previous and Concomitant Medications, Procedures, Follow-up Treatments
    - Previous Medication
    - Concomitant Medication
    - Concurrent Procedures
  - Treatment Compliance and Exposure
    - Duration of Therapy
    - Cumulative Dose, Dose Intensity, Relative Dose Intensity
    - Dose Reductions
    - Therapy Delays
- Safety Data:
  - Display of Adverse Events
    - Overview of Treatment Emergent Adverse Events (TEAEs)
    - Overview of TEAEs Leading to Discontinuation / Dose Reduction of Treatment
    - TEAEs by Primary System Organ Class (SOC) and Preferred Term (PT)
    - Study Intervention Related TEAEs by SOC and PT
    - Serious TEAEs by SOC and PT
    - Non-serious TEAEs by SOC and PT at a Frequency Threshold of 5%
    - TEAEs by Worst Grade, SOC and PT
    - Study Intervention Related TEAEs by Worst Grade, SOC and PT
  - Deaths, Other Serious and Significant Adverse Events

- Deaths by Primary Reason
- Listing of Deaths
- Listing of Serious TEAEs
- Clinical Laboratory Evaluations
  - Hematology - Summary Statistics over Time
  - Hematology - Shift in Toxicity Grading from Baseline to Highest Grade
  - Biochemistry - Summary Statistics over Time
  - Biochemistry - Shift in Toxicity Grading from Baseline to Highest Grade
- Other Safety Evaluations
  - Vital Signs Results Summary Statistics Over Time
  - ECG Results - Summary Statistics Over Time
- Subject Data Listings:
  - Discontinued Subjects
  - Protocol Deviations
  - Demographic Data
  - Treatment Compliance and Exposure
  - Efficacy Results Data
  - Listing of TEAEs
  - Individual Laboratory Measurements

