### 15.6.2 Electrocardiogram (ECG)

ECG summaries will include all ECG assessments from the on-treatment period. All ECG assessments will be listed, and those collected outside the on-treatment period will be flagged in the listing.

The average of the replicate measurements should be determined after the derivation of the individual parameter at each time point.

The analysis of QT data is complicated by the fact that the QT interval is highly correlated with heart rate. Because of this correlation, formulas are routinely used to obtain a corrected value, denoted QTc, which is independent of heart rate. This QTc interval is intended to represent the QT interval at a standardized heart rate. Several correction formulas have been proposed in the literature. For this analysis we will use some of those methods of correction, as described below.

The QT interval corrected for heart rate by the Fridericia's formula, QTcF, is defined as

$$QTcF = \frac{QT}{\sqrt[3]{RR}} ,$$

where RR represents the RR interval of the ECG, in seconds, and can be estimated as 60/Heart Rate.

---

Data will be summarized using QTcF, results will be listed.

The following analyses will be performed for each applicable ECG parameters (RR, PR, QRS, QT, ventricular rate -denoted as HR in what follows-, and QTc), during the on-treatment period. Unscheduled ECG measurements will not be used in computing the descriptive statistics for change from baseline at each post-baseline time point. However, they will be used in the analysis of notable ECG changes and QT parameters.

- For each of the ECG parameters (HR, and QT, QTc, QRS, PR intervals), descriptive statistics at baseline, at each post-baseline time point and changes from baseline at each post-baseline time point
- Frequency (number and percentage) of participants with notable ECG values according to the following categories. The denominator to calculate percentages for each category is the number of participants evaluable for the category:
  - QT/QTc increase from baseline  $>30$  ms,  $>60$  ms
  - QT/QTc  $> 450$  ms,  $> 480$  ms,  $> 500$  ms
  - HR  $\leq 50$  bpm and decrease from baseline  $\geq 20$  bpm
  - HR  $\geq 120$  bpm and increase from baseline  $\geq 20$  bpm
  - PR  $\geq 220$  ms and increase from baseline  $\geq 20$  ms
  - QRS  $\geq 120$  ms

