Complete ECG profiles will be listed for participants with at least one notable ECG interval value or change. Also, qualitative ECG abnormalities will be listed for each participant and time point and the corresponding notable values and abnormality findings will be included in the listings.

**16**

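### The synoptic CSR list in SAP 7.1 keeps ECG summaries by time point, but names no ECG output that counts or identifies participants crossing the protocol's QTcF limits

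*SAP*

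**What the plan says.** SAP 7.1 cuts the scope of analysis after the xevinapant trials were discontinued and lists what is wanted for a synoptic CSR. Under other safety evaluations the only ECG entry is "ECG Results - Summary Statistics Over Time". The participant-level listings at the end of 7.1 include TEAEs and laboratory measurements but no ECG listing.

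SAP 15.6.2 is wider. It opens with "ECG summaries will include all ECG assessments from the on-treatment period" and then specifies:

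- for each ECG parameter, "descriptive statistics at baseline, at each post-baseline time point and changes from baseline at each post-baseline time point";
- a frequency table of participants with notable values, including QT/QTc above 450, 480 and 500 ms and increases above 30 and 60 ms;
- a general listing: "All ECG assessments will be listed, and those collected outside the on-treatment period will be flagged in the listing";
- a targeted listing: "Complete ECG profiles will be listed for participants with at least one notable ECG interval value or change";
- a further listing in which "qualitative ECG abnormalities will be listed for each participant and time point".

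On unscheduled ECGs it says "Unscheduled ECG measurements will not be used in computing the descriptive statistics for change from baseline at each post-baseline time point", followed by "However, they will be used in the analysis of notable ECG changes and QT parameters".

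Protocol 8.2.3 treats a QTcF above 500 ms, or a rise of 60 ms over baseline, as significant prolongation. Confirmed cases lead to electrolyte checks, repeat ECGs and referral to a cardiologist. Protocol 6.8.2 says the effect of xevinapant on QTc is not yet fully known.

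**The concern.** QTc risk is judged participant by participant: what matters is how many crossed a limit, who they were and when. Means, medians and extremes by visit do not answer that. If the synoptic CSR contains only what 7.1 names, a reader could see from a maximum that somebody exceeded 500 ms at a scheduled visit, but could not tell how many participants did so or which ones. An increase above 60 ms found on an unscheduled ECG would not enter the change-from-baseline statistics at all. The reader would then depend on the investigator having recorded the finding as an adverse event.

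**Working it through.** There is no sample size or power figure to reproduce. The check is a comparison of sections with some simple counts.

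**1. Which section governs.** SAP 6.2 called for every analysis in the protocol and the IAP. SAP 7.1 says the Section 6 analyses will not be run as first planned and puts its own list in their place. Sections 14 and 16 are marked as not conducted; 15.6.2 is not. That missing mark is weak evidence that all of 15.6.2 survives, because Section 15 is kept only in part. The vital-sign category shifts (15.5) and the eDISH plots (15.4.2) are likewise unmarked and likewise absent from 7.1. The natural reading is that 7.1 selects the outputs and Section 15 supplies the methods for those selected.

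**2. ECG outputs, side by side.**

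| Output in SAP 15.6.2 | Named in SAP 7.1? |
|---|---|
| Descriptive statistics by time point | Yes |
| Notable-value frequency table | No |
| Listing of all ECGs | No |
| Complete profiles, participants with a notable value | No |
| Listing of qualitative abnormalities | No |

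Named: 1 of 5. The fourth row is a subset of the third, so the tally is descriptive only.

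**3. Notable-value criteria.** QT/QTc increase 2, QT/QTc level 3, heart rate low 1, heart rate high 1, PR 1, QRS 1: 2 + 3 + 1 + 1 + 1 + 1 = 9. QT/QTc criteria: 2 + 3 = 5. None is named in 7.1.

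**4. What the retained statistics can show.** Protocol Table 14 schedules ECGs at screening, C1D1 (predose and postdose) and C1D8 (predose and postdose). If the C1D1 predose ECG is the baseline, there are 3 post-baseline time points; if the screening ECG is, there are 4. The SAP baseline definition is blacked out, so this is an assumption. Protocol 9.4 includes the minimum and maximum among the usual statistics. A maximum above 500 ms at a time point means at least one participant crossed. It gives no count and no identity, and the same maximum at several time points could come from one person or several.

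**5. Unscheduled ECGs.** They are kept out of change from baseline. Absolute values are not expressly excluded, and the section's opening sentence points the other way. Even if they were included, the statistics are by time point and give no worst on-treatment value per participant. The notable-value table is the specified ECG summary in which a late increase above 60 ms would be counted.

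**6. Comparison with other domains.** For hematology and biochemistry, 7.1 keeps both the summaries over time and the shift to the highest grade, plus individual measurements. SAP 15.4.1 (laboratory) and 15.5 (vital signs) also call for on-treatment maximum and minimum. The ECG text in 15.6.2 has no equivalent in its descriptive statistics.

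**7. What cannot be seen.** SAP Section 9, SAP 15.3.3, one item of the AE overview, the protocol's AESI lists, Tables 7 and 8 and some QTcF actions are blacked out.

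**The case against.** The strongest reply is that 7.1 is a deliberate trimming for a programme stopped for lack of benefit, and that ECG was trimmed along with other domains. Protocol 9.4.2 plans no ECG analysis, and no ECG or QTc endpoint appears in the visible objectives. The notable-value table was an addition in the SAP. The limits in protocol 8.2.3 are there to manage participants; they are not analysis thresholds. The retained TEAE tables (by term, worst grade, relatedness and action taken) and the TEAE listing would give both number and identity for any QT event recorded as an AE. A confirmed prolongation that sends a participant to a cardiologist would plausibly be recorded. SAP Section 4 also allows unplanned analyses if the CSR identifies them.

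Most of this stands, and it keeps the point small. What does not fall away is that protocol Appendix 7 leaves it to the investigator's judgment whether an abnormal ECG is clinically significant enough to be an AE, and the documents do not show how the reported grades map to the protocol's QTcF limits. A count from the ECG data does not depend on that judgment.

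A reader might infer that 7.1 and 15.6.2 contradict each other. The documents do not support that firmly: 7.1 reads as a selection, and the missing cancellation mark is explained by Section 15 being only partly kept. A reader might also note that scheduled ECGs end on Day 8, with 6 × 14 = 84 planned dosing days and 84 − 8 = 76 (76/84 = 90%) still to come, and conclude that 7.1 drops 90% of the ECG information. It does not. That figure describes the protocol's ECG schedule, and the proposed table adds no ECGs.

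**Conclusion.** On the reading that 7.1 governs, no ECG output it names counts or identifies participants with QTcF above 500 ms or an increase above 60 ms. Within the 7.1 list, such cases would surface only as recorded TEAEs, or as an unattributed maximum at a scheduled C1D1 or C1D8 time point. This is a limited gap in a deliberately reduced report, and closing it is an optional improvement.

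The documents do not show that any unscheduled ECG was recorded, that any participant crossed a limit, or that data were lost or withheld. A reader might infer selective reporting from SAP version 2.0 (14 March 2025) being dated after the database lock of 20 September 2024. The stated reason for the reduction is the review of the TrilynX data, and nothing points to ECG results.

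Confidence is high for the comparison of the two sections. It is lower for the practical consequence, because dedicated QTc reporting could sit in the blacked-out text.

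**What to change.** In SAP 7.1, under other safety evaluations, add the notable-value frequency table from 15.6.2: QTcF above 450, 480 and 500 ms, and increases above 30 and 60 ms, using scheduled and unscheduled on-treatment ECGs. Under the participant-level listings, add the 15.6.2 listing of complete ECG profiles for participants with a notable value. Both are already specified, so no new data, visits or definitions are needed. The cost is one extra table and one extra listing in a report meant to be short.

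Marking the remaining ECG outputs in 15.6.2 as cancelled, in the style of Sections 14 and 16, would help programmers but is editorial only.
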